The number of outbreaks per arm will be collected from VESUV. At the start of the evaluation period, we will ask participating hospitals to submit the number of full-time positions per included ward. The number of inpatients per ward per day will be obtained from NPR. The number of positions and inpatients will be used as denominators when estimating the secondary attack rate in outbreaks. The number of patients registered in NOIS will be compared to the number of daily inpatients registered in NPR. If the number of inpatients per day changes over time, we will make a new collection of the number of full-time positions to capture significant changes in the organization and size of included wards.

NOIS and NOIS-POSI are surveillance systems where numerators and denominators are registered. From these systems, it is sufficient to receive the results for each ward in the form of the proportion of patients with different types of infections.

From NPR, we will apply for data for all hospitalized patients at both intervention and control wards from and including 1. January 2020 up to the time of application in 2024, giving numerators and denominators for the periods before, during and after the intervention.

When comparing intervention and control groups, we will estimate relative risk (RR) and absolute risk difference (ARF) with 95% confidence intervals (table 2). We will report two-sided p-values where applicable and use the significance criterion p<0.05.

We will use modified Poisson regression to compare hand hygiene compliance one year after NOST was introduced in the intervention wards³. We will adjust for the factor used in stratification (hospitals) as a fixed effect.

Compliance will be analyzed and reported for each occupational group and total for all healthcare personnel. Outbreaks will be analyzed and reported as the number of outbreaks and secondary attack rate per arm, in total and distributed by patients and staff. The incidence of infection in patients will be analyzed and reported in total and by types of infection.

A more detailed description of the analyzes of the main and secondary outcomes will be published in a separate analysis plan.

[figure not shown]

Figure 1. Overview and schedule for the intervention and measurements in the evaluation

Table 2. Dummy table with results for compliance with hand hygiene recommendations

	Intervention arm	Control arm	ICC	Adjusted RR (95% CI)	ARF (95% KI)	p-value
Primary outcome						

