Compliance hand hygiene	540/900 ¹ (0.60)	369/900¹ (0.41)	0.020	1.683 (1.654 – 1.713)	0.279 (0.270-0.288)	<0.05

¹Number of hand hygiene performed by indicated events

Sample size

Sample size calculation (number of wards needed in each arm) is based on the following:

- Type I error rate: 0.05
- Power: 0.80
- Primary outcome is dichotomous with expected baseline proportion: 0.40
- Outcome is measured as simple difference at the end of the intervention period
- Intraclass correlation coefficient (ICC) of primary outcome: 0.10
- Expected number of measured events per cluster (hospital ward): 30
- Degrees of freedom used when adjusting for cluster-level covariates in the analysis: 2
- A priori stratification in the design and analyses
- Hypothesized intervention effect (increased proportion of compliance): 0.20

The estimation of necessary number of wards in both arms is conducted in parallel cluster-randomized trials calculator published by the National Institutes of Health (https://researchmethodsresources.nih.gov/grt-calculator).

Table 3 shows the function of the number of clusters (wards) per arm, and the number of events measured in each ward. The first row shows the number of clusters, while the first column shows the number of events measured per ward. The inner cells show the magnitude of the difference (increase in proportion) that we can identify as significant with a power of 80%. We assume that we

can detect a difference of at least 20%, and the calculations show that we have enough power for this if we have 26 wards in each arm, if there are 30 hand hygiene sessions measured in each ward.

Table 3. Detectable difference in the arms, distributed by number of participating wards per arm and number of events measured per ward

Absolute Detectable Difference Clusters (wards) per arm

		24	25	26	27	28
Events measured per ward	15	0,2266	0,2219	0,2175	0,2134	0,2094
	23	0,2113	0,2069	0,2028	0,199	0,1953
	30	0,2042	0,2	0,1961	0,1923	0,1888
	38	0,1992	0,1951	0,1912	0,1876	0,1841
	45	0,1962	0,1922	0,1884	0,1848	0,1814

Group allocation

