The primary outcome is compliance with hand hygiene recommendations by hospital employees who do patient-related work. Compliance will be assessed one year after randomization by trained and experienced observers. The observers will record the number of observations made and the number of these observations that meet the criteria for compliance. The number of observations and compliances will be measured at the level of hospital ward. Compliance will therefore be aggregated at the level of hospital ward and the primary outcome is a count variable.

161 **5.2 Secondary outcomes**

As for the primary outcome, all secondary outcomes will be aggregated at the level of hospital ward.
Unlike the primary outcome, all secondary outcomes are measured over the one-year trial period
rather than at the end of the trial.

165

Sec	ondary Outcome	Туре	Denominator	Data source			
Infe	Infectious disease outbreaks						
1.	Outbreak	Count	Wards	VESUV			
2.	Inpatient infection	Count	Inpatients in wards with outbreaks				
3.	Employee infection	Count	Employees in wards with outbreaks				
Sur	veillance of HAI						
4.	Inpatient infection	Count	Inpatients included in	NOIS			
			the surveillance				
5.	Inpatient antibiotic treatment	Count	Inpatients included in				
			the surveillance				
Sur	veillance of postoperative site infectior	15					
6.	Inpatient treatment for postoperative	Count	Surgical inpatients	NOIS-POSI			
	site infection		included in the				
			surveillance				
HAI	diagnoses						
7.	Inpatient HAI diagnosis	Count	Inpatients in the study period	NPR			
Len	gth of hospital stay						
8.	Bed-days per inpatient per stay	Continuous		NPR			

166 167

168 6 Sample Size

169 Assuming $\alpha = 0.05$, $\beta = 0.8$, a control risk of 0.4, an intervention risk of 0.6 (i.e., the treatment effect 170 is a risk difference of at least 0.2), an ICC of 0.1, an average cluster size of 30 observations among 171 hospital employees who do patient-related work, a loss of 2 d.f. for adjustment of cluster-level 172 covariates, and stratification by hospital, it was estimated that at least 52 hospital wards should be 173 recruited (26 in each arm).

7 General Analysis Considerations

175 **7.1 Timing of Analyses**

176 Analyses will be performed after the database is locked. No interim or follow-up analyses are planned.

177 7.2 Analysis Sets

Although this SAP defines three populations, there is only a single analysis set that will contain all

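### Table 3 and the 26 wards per arm do not follow from the stated simple end-of-period difference: the detectable differences are about 1.4 times too large, an error on the conservative side

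*Protocol*

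**What the plan says.** The inputs are listed in the protocol under Sample size:

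- "Type I error rate: 0.05", with power 0.80. Two-sided testing is stated for the analysis under Data collection and outcomes: "We will report two-sided p-values where applicable and use the significance criterion p<0.05".
- "Primary outcome is dichotomous with expected baseline proportion: 0.40"
- "Hypothesized intervention effect (increased proportion of compliance): 0.20"
- "Outcome is measured as simple difference at the end of the intervention period"
- "Expected number of measured events per cluster (hospital ward): 30"
- ICC 0.10, 2 degrees of freedom for cluster-level covariates, and a priori stratification with no number of strata given.

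From these the protocol derives Table 3, which prints 0.1961 at 26 wards per arm and 30 events, and states that "the calculations show that we have enough power for this if we have 26 wards in each arm". That sentence then makes the result depend on 30 hand hygiene sessions per ward, whereas the input list and Table 3 count events. SAP section 6 repeats the inputs and gives a minimum of 52 wards to be "recruited (26 in each arm").

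The design matches the stated contrast. Under Data collection and outcomes, intervention wards at one year are compared with control wards measured for the first time at that point.

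**The concern.** The required number of wards, the detectable difference and the implied power are the headline planning figures of both documents. A reader should be able to recover them from the listed inputs. Here no cell of Table 3 can be recovered under the stated contrast. Control wards have no earlier measurement, so a before-after net difference cannot be formed in this trial, and the SAP section 9.1 model uses only the end-of-trial counts for the primary outcome. As printed, the table understates what a given number of wards can detect, and it presents 26 per arm as roughly the minimum when the stated inputs imply about half that.

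**Working it through.** **Inputs.** All are from the protocol's Sample size section, with sidedness from Data collection and outcomes: p = 0.40, so p(1−p) = 0.24 (also 0.24 at 0.60); ICC = 0.10; m = 30 events per ward; two-sided alpha 0.05; power 0.80; 2 df for covariates; g wards per arm. The design effect is 1 + 29 × 0.10 = 3.9.

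**Step 1: reproduce the printed table.** The formula that fits is

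d = (t₀.₉₇₅,df + t₀.₈₀,df) × √{4p(1−p)[1+(m−1)ICC]/(mg)}, with df = 4(g−1)−2.

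At g = 26 and m = 30:

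- df = 98 and the t-sum is 1.9845 + 0.8453 = 2.8298.
- The standard error is √(4 × 0.24 × 3.9/780) = √0.0048 = 0.0693.
- d = 2.8298 × 0.0693 = 0.1961, as printed.

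This formula matches all 25 cells to four decimals. At g = 25 it gives 0.20002, printed as 0.2 but just above the target, which would explain why 26 was chosen and not 25.

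**Step 2: apply the stated simple difference.** For two arms compared once,

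d = (t₀.₉₇₅,df + t₀.₈₀,df) × √{2p(1−p)[1+(m−1)ICC]/(mg)}, with df = 2(g−1)−2.

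At g = 26 and m = 30:

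- df = 48 and the t-sum is 2.0106 + 0.8492 = 2.8598.
- The standard error is √0.0024 = 0.0490.
- d = 2.8598 × 0.0490 = 0.1401.

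| Wards per arm (m = 30) | 24 | 25 | 26 | 27 | 28 |
|---|---|---|---|---|---|
| Table 3 | 0.2042 | 0.2000 | 0.1961 | 0.1923 | 0.1888 |
| Simple difference | 0.1461 | 0.1430 | 0.1401 | 0.1374 | 0.1348 |

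Over all 25 cells the ratio of printed to simple-difference value runs from 1.398 to 1.401. That is √2 on the standard error, slightly offset by the larger df.

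**Step 3: rule out other explanations.** At 26 wards and 30 events, keeping the simple difference:

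- One-sided testing gives 0.124.
- Variance 0.25 in place of 0.24 gives 0.143.
- Using each arm's own variance gives 0.141.
- Taking up to 30 df for covariates gives at most 0.144.
- No single other ICC fits the table. In the column for 26 wards it would have to be 0.264 at m = 15 but 0.218 at m = 45.

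Fitting the printed cells against 1/m returns an ICC of 0.100, so the ICC was entered as stated.

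**Step 4: wards and power on the stated inputs (simple difference, noncentral t).**

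| Wards per arm | Detectable difference at 80% power | Power for 0.20 |
|---|---|---|
| 13 | 0.203 | 78.8% |
| 14 | 0.195 | 82.0% |
| 26 | 0.140 | 97.9% |

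A normal approximation agrees: 97 observations per arm × 3.9 / 30 = 12.6, so 13 wards, or 13.9, so 14, with continuity correction.

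**Step 5: what 26 per arm does protect against.** With g = 26 and m = 30, the simple-difference detectable value reaches 0.200 at an ICC of about 0.24 (design effect 1 + 29 × 0.24 = 7.96).

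**Step 6: sessions or events.** The protocol's Intervention section says a session often holds 7 to 20 indications, so 30 sessions would be about 210 to 600 events. The input list, Table 3, the minimum of 30 observations per ward under Data collection and outcomes, and SAP section 6 all use events or observations.

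**The case against.** Four objections deserve weight.

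**The cause is not shown.** A reader might infer that the calculator was set to a net (before-after) difference. The documents give neither settings nor output. The doubled variance and its df fit a difference between two differences, but they would also fit another four-cell contrast, for instance one arising from the declared stratification, whose number of strata is not given. This objection stands: only the mismatch is established.

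**The sufficiency claim is still true.** A reader might infer that the trial is mis-sized or underpowered. It is not, on this account. On the stated inputs 26 per arm is more than enough, and the SAP's minimum of 52 wards is sufficient too. This also stands. What fails is the values in Table 3 and the implication that about 26 is the number needed for 80% power.

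**The practical effect is small.** Under Group allocation the protocol expects several hundred wards, and SAP section 11 reports 95% confidence intervals, from which a null result would be read. This limits the consequence, but the figures still need correcting.

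**The corrected figures could look too favourable.** They rest on one ward-level ICC of 0.10. SAP section 4.1 says the same person may be observed in several sections, SAP section 7.3 expects clustering within hospital, and whole hospitals may be excluded after randomization. This is a good reason to state the new figures as conditional. It does not justify the old ones, because neither document presents 26 as a deliberate margin.

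**Conclusion.** The point holds. Table 3 and the derivation of 26 wards per arm do not follow from the stated inputs and contrast. The printed detectable differences are about 1.40 times the simple-difference values: 0.1961 against 0.140 at 26 wards and 30 events. Power for 0.20 at that size is about 98%, against the 80% planned for, and 14 per arm would suffice. These results assume two-sided alpha 0.05, ICC 0.10, 30 events in every ward, 2 df for covariates, and no clustering beyond the ward. The error is conservative, threatens neither validity nor power, and calls for no more wards. Which calculator setting produced it remains unknown.

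**What to change.** 1. Rerun the calculation as a post-only simple difference, state every calculator setting including the number of strata, and replace Table 3.
2. In the protocol's Sample size section and SAP section 6, do one of the following:
   - restate the figures as conditional on ICC 0.10: 26 wards per arm with 30 events detects 0.14 at 80% power, or gives about 98% power for 0.20; or
   - keep 26 per arm and describe it explicitly as a margin that holds 80% power for 0.20 up to an ICC of about 0.24.
3. In the sentence below the reference to Table 3, change sessions to events.

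The cost is one calculator run and wording in two documents. Recruitment, data collection and analysis are unaffected.

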POSI	Postoperative site infection			
RD	Risk difference			
RR	Risk ratio			
VESUV	Norwegian Institute of Public Health's web-based outbreak notification system			

65 **3 Introduction**

66 **3.1 Preface**

Effective infection prevention and control (IPC) is essential to ensure high-quality healthcare services. Infections that occur during hospitalization and because of services provided may interfere with the outcome of needed medical treatments. To prevent healthcare-associated infections (HAIs), it is essential that all healthcare personnel are well trained in and follow standard IPC measures during patient care. Standard precautions include hand hygiene, use of personal protective equipment and more.

73

The Norwegian Institute of Public Health (NIPH) is introducing a new electronic tool and national template for direct observation of compliance with recommended IPC measures in healthcare. The solution is called the National Tool for Observation of Infection Prevention Measures (NOST). NOST is a quality improvement tool that includes a web-based solution for observing and recording the degree of compliance with recommendations for hand hygiene and other IPC measures.

79

80 The trial protocol is available at https://zenodo.org/records/7648821

81 3.2 Research Questions

82 Would risk of compliance with hand hygiene recommendations by employees who perform patient-83 related work in Norwegian hospital wards (*population*), measured at one-year postimplementation 84 (*primary outcome*), be different if wards were to implement and adhere to NOST (*intervention*) 85 compared to if NOST was not implemented and not adhered to (*control*)?

86

Would risk of outbreaks and infections among inpatients at Norwegian hospitals, measured over one year postimplementation (*example secondary outcomes*), be different if wards were to implement
 and adhere to NOST (*intervention*) compared to if NOST was not implemented and not adhered to
 (*control*)?

91

92 These questions are about the effect of implementing and adhering to NOST, not the effect of a policy 93 that a ward should implement NOST. This has important implications for the estimands and 94 estimators.

Study Methods 96 4

General Study Design and Plan 97 4.1

98

Populations	 Employees in Norwegian hospitals who perform patient-related work. Inpatients in Norwegian hospitals. Norwegian hospital wards. 				
Intervention	Implementing NOST				
Control	Not implementing NOST				
Primary outcome	Compliance with hand hygiene recommendations by hospital employees who do patient-related work, measured at one year after randomization.				
Design	Cluster-randomized parallel two-arm superiority trial.				
Blinding	Trial participants and other personnel cannot be blinded to treatment allocation. The trial statistician will be blinded to treatment allocation.				
Treatment allocation	Hospital wards will be randomized 1:1. Randomization will be stratified by hospital to ensure approximately equal allocation of wards within hospital.				

99

101

The following table shows the structure of data registered in NOST: 104

1	n	5
т	υ	J

Plac	Place Observation of hand hygiene			2	Person	
Hospital	Ward	Section number	Observation number	Indication	Compliance	Profession
1	5	1	1	А	1	Nurse
			2	В	1	
			3	D	0	
1	4	2	4	В	1	Physician
2	2	3	5	А	0	Nurse
			6	В	1	
			7	С	0	
			8	С	0	
			9	E	1	
1	5	4	10	A	1	Nurse
			11	E	1	assistant

- 107 Description of the variables:
- Hospital: a unique ID-number for each hospital. The data will also include information about
 the actual health trust and health region
- Ward: a unique ID-number for each ward within the actual hospital. The wards will be allocated to intervention and control arms
- Section number: a unique running number for a section of observations where the observer has followed a person and registered all hand hygiene indications happening within a specific setting or task. A section will most often include several observations where the person has or should have performed hand hygiene.
- Observation number: a unique running number for an observation where hand hygiene was
 or should have been performed
- Indication: A code for why hand hygiene was advised, based on the guidelines by the World
 Health Organization
- Compliance: A code displaying whether the person performed hand hygiene or not (1 or 0)
 when the indication arose
- Profession: The health profession of the observed person. Other personal information is not registered. Only one person is observed within a section number, but the same persons may be observed in several sections
- 125

126 4.2 General Study Populations and Inclusion-Exclusion Criteria

127 There are three general study populations (see above and the study protocol). This SAP introduces a 128 third population not specified in the protocol, hospital ward. This was introduced because one of the 129 secondary outcomes (outbreaks) cannot be measured at the level of employee or inpatient but can 130 be measured at the level of ward.

- 131
- We will exclude hospitals and their associated randomized wards from all analyses if the hospital after randomization decides not to implement or to terminate the execution of NOST, and the decision is communicated to the Norwegian Institute of Public Health.
- 135

136 **4.3 Treatment Allocation**

Stratified randomization will be used to allocate wards to 1:1 intervention and control arms. Randomization will be stratified by hospital. Randomization will be performed using a computer-based system and the investigators will not be able to manipulate treatment allocation. The approach is outlined in the protocol.

141 **4.4 Blinding/Masking**

142 It is not possible to blind trial participants or observers to treatment allocation. While much of the 143 outcome data will be obtained from registries (e.g., to which events are notified), the people who 144 report data may not be blinded to treatment allocation. However, the trial statistician who will analyze 145 the data will be blinded to treatment allocation.

146

147 When all data have been collected, a member of the research group will apply a blind to the treatment 148 allocation variable, so that the statistician will not know which arms correspond to the intervention 149 and control treatments. The analysis of the primary outcome will be performed blinded. Before 150 unblinding, we will publish a short document on Zenodo describing how the result for the primary 151 outcome was interpreted by the project team. The blind will then be removed and the secondary

analyses will be performed unblinded.

153 **5 Outcomes**

154 **5.1 Primary outcome**

The primary outcome is compliance with hand hygiene recommendations by hospital employees who do patient-related work. Compliance will be assessed one year after randomization by trained and experienced observers. The observers will record the number of observations made and the number of these observations that meet the criteria for compliance. The number of observations and compliances will be measured at the level of hospital ward. Compliance will therefore be aggregated at the level of hospital ward and the primary outcome is a count variable.

161 **5.2 Secondary outcomes**

As for the primary outcome, all secondary outcomes will be aggregated at the level of hospital ward.
Unlike the primary outcome, all secondary outcomes are measured over the one-year trial period
rather than at the end of the trial.

165

Sec	ondary Outcome	Туре	Denominator	Data source			
Infe	Infectious disease outbreaks						
1.	Outbreak	Count	Wards	VESUV			
2.	Inpatient infection	Count	Inpatients in wards with outbreaks				
3.	Employee infection	Count	Employees in wards with outbreaks				
Sur	veillance of HAI						
4.	Inpatient infection	Count	Inpatients included in	NOIS			
			the surveillance				
5.	Inpatient antibiotic treatment	Count	Inpatients included in				
			the surveillance				
Sur	veillance of postoperative site infectior	15					
6.	Inpatient treatment for postoperative	Count	Surgical inpatients	NOIS-POSI			
	site infection		included in the				
			surveillance				
HAI	diagnoses						
7.	Inpatient HAI diagnosis	Count	Inpatients in the study period	NPR			
Len	gth of hospital stay						
8.	Bed-days per inpatient per stay	Continuous		NPR			

166 167

168 6 Sample Size

169 Assuming $\alpha = 0.05$, $\beta = 0.8$, a control risk of 0.4, an intervention risk of 0.6 (i.e., the treatment effect 170 is a risk difference of at least 0.2), an ICC of 0.1, an average cluster size of 30 observations among 171 hospital employees who do patient-related work, a loss of 2 d.f. for adjustment of cluster-level 172 covariates, and stratification by hospital, it was estimated that at least 52 hospital wards should be 173 recruited (26 in each arm).

7 General Analysis Considerations

175 **7.1 Timing of Analyses**

176 Analyses will be performed after the database is locked. No interim or follow-up analyses are planned.

177 7.2 Analysis Sets

Although this SAP defines three populations, there is only a single analysis set that will contain all
wards randomized and not excluded (see exclusion criteria, above). In practical terms, the data set
will have one ward per row and there will be 9 outcome variables (columns), plus covariates.
Outcomes will be analyzed in the arms to which the wards were randomized.

182 **7.3 Covariates and Subgroups**

183 Because randomization is stratified by hospital, we originally planned to adjust for hospital as a fixed 184 effect in all analyses. However, the planned adjustment would require estimating one parameter for 185 each hospital (minus the reference hospital), in addition to treatment effect. The large number of parameters that would therefore need to be estimated could lead to imprecision on the effect 186 187 estimates and possibly also estimation problems. Further, the trial is unlikely to include all hospitals 188 in Norway and hence the sample will not exhaust all possible levels of the hospital variable. For these 189 reasons, and the chosen regression model (see section 9), we will account for the likely clustering of 190 outcomes within hospital using cluster-robust standard errors, with hospital as the cluster variable.

191

192 We will obtain data on the following variables to support four subgroup analyses:

- 193
- 194 1. Hospital department (e.g., psychiatry, orthopedics, neurology, ...)
- 195 2. Employee profession (e.g., physician, nurse, ...)
- 196 3. Indications of hand hygiene (e.g., before patient contact, after exposure to body fluid,)
- 197

198 These subgroups are based on the hypothesis that baseline hand hygiene compliance may differ by 199 type of ward or type of profession with different levels of education or work tasks, and compliance 200 may vary depending on the situations in which hand hygiene is recommended. It may be the case that 201 treatment effect is different in these subgroups. (For example, if some ward types already have 202 exceptionally high baseline compliance with hand hygiene recommendations, then only a small 203 beneficial treatment effect is possible for this subgroup. Conversely, if a type of ward or profession 204 has exceptionally low baseline compliance for all or some of the indications then a large beneficial 205 treatment effect may be achievable in this subgroup.

206

207 7.4 Multiple Centers

We will not combine outcomes by ward or hospital (i.e., we will not define "pseudo-centers"). We will not explore treatment-by-hospital interactions. Between-hospital differences in risk of compliance, for example, will be accounted for using cluster-robust standard errors with hospital as the cluster variable.

212 **7.5 Missing Data**

We will examine the data for spurious values and seek to verify or obtain correct values if data are miscoded (e.g., negative counts, nonintegral values entered for counts, or counts that appear to be unrealistically large). We will report any data processing decisions that need to be made at the time of analysis.

217

218 It is very unlikely that data will be missing for the treatment, hospital, or ward variables, which are219 needed in all analyses.

- 220
- 221 Data may be missing for the primary outcome variable, which is measured by observers. It is unlikely

- that data will be missing for the secondary outcome variables, which will be obtained from registries,
 but data will be missing if hospitals do not provide data to the registries (Norwegian Institute of Public
- 224 Health).
- 225

If wards do not provide outcome data for the primary outcome, we will contact them and ask them to provide the missing data. If more than 5% of wards do not provide primary outcome data, we will use Little's test to assess if the data are unlikely to be missing completely at random (MCAR) but missing at random (MAR). If we assess the data to be MAR, we will use multiple imputation by chained equations (MICE) and perform the prespecified analyses including all wards.

231

The primary outcome comprises counts of observations and counts of those observations that meet the criteria for compliance. We anticipate that both counts will be missing for wards that do not provide outcome data. It will therefore be necessary to impute missing values for these variables in a way that ensures both are valid counts, and that the number of compliances is not greater than the number of observations imputed for a given ward. We will do this as follows.

237

238 For each ward with non-missing primary outcome data, we will compute a point estimate of the 239 logit risk of compliance as $w_i = \log r_i - \log(1 - r_i)$, where $r_i = n_i/N_i$. Within the MICE 240 framework, we will impute logit risks for wards with missing primary outcome data (e.g., using a linear 241 model with normal errors), and hence risks for wards with missing primary outcome data as $r_i = 1/(1 + e^{-w_i})$, where w_i is an imputed logit risk. Missing observation counts (N_i) will be modelled 242 using a Poisson model. This may impute that no observations were made in some wards. We will 243 244 address this issue by replacing zero observation counts with ones. Finally, we will impute the number of compliances for the wards with missing primary outcome data as the passive variable $|N_i r_i + 1/2|$ 245 246 (i.e., "rounding half up" a possibly non-integral number of imputed compliances to an integer), where 247 N_i and r_i are imputed as described above. The r_i will not be used in subsequent analyses.

- 248
- 249 The imputation model for the primary outcome will include:
- 250251 Treatment assignment
- Adherence (if available; see section 7.6)
- Hospital (assuming data are not missing for all wards in a hospital)
- Hospital region
 - Type of department
 - The secondary outcomes (on the basis that the primary outcome is likely to be highly correlated with other outcomes)
- 257 258

255

256

259 If we cannot assess that the data are likely MAR and cannot rule out the possibility that the data are 260 missing not at random (MNAR), we will perform complete case analyses, but will not draw strong 261 conclusions about the causal effect of NOST and report the missing data as a possible limitation.

262

263 The secondary outcomes depend on registry data. It is possible that some wards or hospitals will either 264 never report data or will intermittently report data. Both possibilities represent missing outcome data 265 problems. We will therefore follow the same general approach as for missing primary outcome data. 266 In the case that secondary outcome data is known to be intermittently reported (i.e., data for some collection periods are available for certain wards, but no data have been reported by the wards for 267 268 other periods), we will use MICE to impute for the collection periods with missing data and then 269 compute the total number of inpatients infected (for example). The imputed outcome is therefore a function of imputed variables (a "passive" variable), which should be handled carefully in the analysis. 270 271 In Stata, it is necessary to use the syntax "mi passive: generate..." or 272 "mi register passive...", prior to "mi estimate:..." to ensure the passive variables are generated correctly in the imputed data sets. In R, passive variables can be handled using the approach
described in section 3.4 of van Buuren and Groothuis-Oudshoorn [1].

275

276 Unless legally or ethically prohibited, we will report any missing data and wards or hospitals that 277 cannot be included in analysis, for example due to withdrawal from the trial.

278 7.6 Intercurrent Events

279 Recall from section 3.2 that the research question is about the effect of implementing and adhering 280 to NOST. We anticipate that some wards may not adhere or fully adhere to the treatment to which 281 they were randomized. For example, a ward may have been randomized to implement and adhere to 282 NOST for the one-year period of the trial, but either did not implement NOST or did not fully adhere. 283 Similarly, a ward may have been randomized to the control arm (i.e., to not implement NOST), but 284 NOST was partially or fully implemented. Because such events would occur after randomization and 285 would change the interpretation of the outcome from that originally intended and hence give a 286 treatment effect estimate that does not have the intended interpretation, non-adherence can be 287 treated as an intercurrent event (ICE) [2].

288

All estimands (see section 9) for which statistical analyses will be performed utilize collapsible measures of effect (risk ratio or mean difference). This allows any non-adherence to be addressed via regression adjustment. We will measure adherence using the proportion of time after randomization and up and including the final data collection period (i.e., adherence will be measured using a value between 0 and 1, inclusive).

294

If 5% or more wards do fully not adhere to their randomized treatment, we will estimate the effect of being randomized and adhering to NOST as the sum (on the log scale for ratio effect measures) of two effects: randomization to NOST and adherence to NOST. Note that adherence to NOST will also be measured in the control arm to facilitate the estimation of the effect of full versus no adherence to NOST. We will then exponentiate the sum to obtain the desired estimate of treatment effect.

300

301 If fewer than 5% of wards do not adhere to their randomized treatment we will not account for the302 non-adherence, but report it is a possible limitation.

303 8 Summary of Study Data

A CONSORT trial flow diagram will be presented.

305

A table of baseline characteristics will be presented following CONSORT guidelines, as follows. Continuous variables will be summarized using the following descriptive statistics: median and interquartile range (IQR). The frequencies and percentages of observed levels will be reported for categorical variables. Baseline characteristics will be reported in a table like the following:

		Control (N = XXX)	NOST (N = XXX)
Hospitals	N (%)	XXX	XXX
Number of beds	Median [IQR]	XXX [XXX to XXX]	XXX [XXX to XXX]
Health region			
North	N (%)	XXX	XXX
Central	N (%)	XXX	XXX
South-East	N (%)	XXX	XXX
Wards	N (%)	XXX	XXX
Health region			

North	N (%)	XXX	XXX
Central	N (%)	XXX	XXX
South-East	N (%)	XXX	XXX
Department			
Oncology	N (%)	XXX	XXX
Orthopedics	N (%)	XXX	XXX
Neurology	N (%)	XXX	XXX
Profession			
Physician	N (%)	XXX	XXX
Nurse	N (%)	XXX	XXX

Effect estimates for the primary and secondary outcomes will be reported in a table like the following:

	Control	Intervention	Risk Ratio (95% Cl)	p -value	Risk Difference (95% Cl)
Primary outcome					
Compliance	XXX/XXX (XXX%)	XXX/XXX (XXX%)	XXX [XXX to XXX]	0.XXX	XXX [XXX to XXX]
Secondary outcomes					
Outbreaks	XXX/XXX (XXX%)	XXX/XXX (XXX%)	XXX [XXX to XXX]	0.XXX	XXX [XXX to XXX]
Patients infected	XXX/XXX (XXX%)	XXX/XXX (XXX%)	XXX [XXX to XXX]	0.XXX	XXX [XXX to XXX]
			Mean Difference (95% Cl)	p-value	
Bed days/stay	XXX (SD = XXX)	XXX (SD = XXX)	XXX [XXX to XXX]	0.XXX	

Effect estimates for the subgroup analyses for the primary outcome will be reported in a table like the

following:

3	1	9

	Control	Intervention	Risk Ratio (95% CI)	p -value	Risk Difference (95% Cl)
Department					
Psychiatry	XXX/XXX (XXX%)	XXX/XXX (XXX%)	XXX [XXX to XXX]	0.XXX	XXX [XXX to XXX]
Orthopedics	XXX/XXX (XXX%)	XXX/XXX (XXX%)	XXX [XXX to XXX]	0.XXX	XXX [XXX to XXX]
Neurology	XXX/XXX (XXX%)	XXX/XXX (XXX%)	XXX [XXX to XXX]	0.XXX	XXX [XXX to XXX]
Profession					
Physician	XXX/XXX (XXX%)	XXX/XXX (XXX%)	XXX [XXX to XXX]	0.XXX	XXX [XXX to XXX]
Nurse	XXX/XXX (XXX%)	XXX/XXX (XXX%)	XXX [XXX to XXX]	0.XXX	XXX [XXX to XXX]
Indication					
Before patient	XXX/XXX (XXX%)	XXX/XXX (XXX%)	XXX [XXX to XXX]	0.XXX	XXX [XXX to XXX]
contact					
After exposure to	XXX/XXX (XXX%)	XXX/XXX (XXX%)	XXX [XXX to XXX]	0.XXX	XXX [XXX to XXX]
body fluid					

326 8.1 Derived Variables

The secondary outcomes are derived from ongoing notifications or from reports that hospitals should submit for specific periods, e.g. four times a year. For example, the number of HAIs (NOIS) over the one-year trial period would be the sum of such reports. This has implications for imputation, if some hospitals do not report data for one or more of the four-month periods (see section 7.5).

331 8.2 Protocol Deviations

Any deviations from the original protocol or this SAP will be reported and justified.

333 9 Estimation and Analyses

While this trial is cluster-randomized (ward is the cluster), outcome data will be measured at the level of ward. The unit of randomization and the unit of analysis are therefore identical. It is not necessary to account for cluster randomization as in trials where clusters of units are randomized, and outcomes are measured on the units.

338

339 9.1 Risk Ratio Estimation

If fewer than 5% of wards do not adhere to their randomized treatment, we will estimate marginal
 risk ratios (RRs) using binomial regression without accounting for the non-adherence. For the primary
 and most of the secondary outcomes, this is:

- 343
- 344 345

$$n_i \sim B(N_i, p_i)$$
 where $\log p_i = \beta_0 + \beta_X x_i$

With respect to the primary outcome, n_i is the number of compliances in the *i*th hospital ward, N_i is the number of observations made in the *i*th hospital ward, β_0 estimates log risk in control, x_i indicates if the *i*th hospital ward was randomized to NOST, β_X estimates the effect of being randomized to NOST as a marginal log risk ratio. The marginal log risk ratio of being randomized to and adhering to NOST is estimated by β_X .

If 5% or more wards do fully not adhere to their randomized treatment, we will estimate marginal risk
 ratios (RRs) using binomial regression as follows:

354 355 356

 $n_i \sim B(N_i, p_i)$ where $\log p_i = \beta_0 + \beta_X x_i + \beta_A a_i$

357 Here, $0 \le a_i \le 1$ models the degree of adherence by the *i*th hospital ward to NOST (see section 7.6) 358 with $\alpha_i = 0$ corresponding to non-adherence and $\alpha_i = 1$ corresponding to full adherence, and β_A 359 estimates the effect of full adherence to NOST. The marginal log risk ratio of being randomized to and adhering to NOST is estimated by $\beta_X + \beta_A$. Note that the x_i and a_i may be highly correlated (almost 360 collinear) because we expect that most wards that implement NOST will also adhere to NOST. For this 361 reason, we will not interpret β_X and β_A separately. We will assume that the statistical software will 362 cope well with the high correlation but will address this issue during analysis in the case of 363 364 nonconvergence.

365

366 Estimation can be performed using Stata as follows (see footnote 1 on page 14):

367 368 binreg compliances i.treat c.adh, n(observations) rr vce(cluster hospital) 369

370 where data are arranged with one ward per row, compliances is a variable containing the numbers

of observations where the employees comply, treat is a treatment indicator where 1 indicates randomization to NOST, adh is a variable containing adherences (which would be omitted if fewer than 5% of wards do not adhere to their randomized treatment), observations is a variable containing the numbers of observations made, and hospital is a factor variable that codes for the hospital to which the wards belong. Treatment effect can then be estimated on the log scale using:

lincom _b[1.treat] + _b[adh]

379 Estimation can be performed using R as follows:

If the analysis is performed in R after imputation (see section 7.5), the script will be run in a loop
